#### 10.4 The therapeutic Window

The estimated sigmoidal dose-response curve with 95% credibility limits compared to placebo (left-sided y-axis) will be illustrated together with the incidence per 100 person-weeks with 95% confidence limits of observation of serum sodium  $<130$  mmol/L and  $\leq 125$  mmol/L, respectively, at or before 12 weeks (both on the right-sided y-axis). The estimated treatment effects with 95% confidence limits compared to placebo for the groups treated with FE 201836 based on the MMRM model described in Section 10.3.4 will also be presented in the graph. The horizontal x-axis will represent the dose range of FE 201836. The therapeutic window is defined as the dose range where FE 201836 is deemed efficacious while the incidence of hyponatraemia is acceptable. Two illustrations will be made with different estimated dose-response curves for the efficacy of FE 201836: one using the results from the primary analysis and one using Sensitivity Analysis 6 based on the actual treatment received.

The sex-specific therapeutic windows will be illustrated similarly.

The therapeutic window of nocturnal volume will be presented similarly.

In addition, similar illustrations of the therapeutic window will be produced using the estimated treatment contrast compared to placebo for the change from baseline-ENR to lowest post-baseline measurement of serum sodium as the safety indicator. To make the results for the efficacy indicator

and the safety indicator comparable in each of these figures, the same treatment definition and the same analysis set will be used for both indicators in each figure.

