7.1.3.1 Serum Sodium

Serum sodium levels will be monitored throughout the trial as hyponatraemia is a potentially serious adverse drug reaction (ADR) associated with desmopressin treatment and may potentially be associated with FE 201836 treatment.

A central laboratory will be used. However, a local laboratory may be used in addition to the central laboratory if a quick turn-around time of the result is needed. In such case a sample must also be sent to the central laboratory. Evaluation of the laboratory-based eligibility criteria will be determined by the central laboratory results. All serum sodium values must be reviewed as soon as possible after the results are available. Any unexpected low serum sodium value must be re-tested. Any significant changes in serum sodium, judged by the investigator as clinically significant must be reported as adverse events, as described in Section 8.2.

Blood samples for analysis of serum sodium will be collected, preferably in the morning, at Visits 1, 3, 5, 6, 7 and 8, as presented in Table 6-1. The risk for subjects developing hyponatraemia during the trial period will be mitigated as follows (serum monitoring plan):

Screening (Visit 1)

All subjects must have normal serum sodium (≥ 135 mmol/L) at screening (Visit 1). If the serum sodium value is < 135 mmol/L (re-tested and confirmed, with results available within 7 days) the subject must be discontinued from the trial as a 'screening failure'.

Active Run-in Period

During the 1-week active run-in period, 4 days (± 1 day) after the planned start of IMP treatment, the subject will be telephoned to follow-up on safety.

Visit 3

At Visit 3 (after the active run-in), if the serum sodium value is < 130 mmol/L the investigator must immediately contact the subject and schedule visits for further evaluation. If the serum sodium value is < 130 mmol/L (re-tested and confirmed, with results available within 7 days) the subject will not be randomised to the trial and must be discontinued from the trial as a 'screening failure'. The subject will be followed (by the investigator) for safety until the serum sodium level is stable and not clinically significant, preferably until at least ≥ 135 mmol/L.

If the subject cannot attend Visit 3 as planned, arrangements must be made to test the serum sodium level at Day 6-8 from the IMP start date to ensure the serum sodium level is measured while the subject is taking IMP.

12-week Randomised Treatment Period

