**Table 3 Schedule for Assessments of Endpoints According to the Flow Chart in the Protocol.**

Capital X Shows Endpoint-Analyses Time Points, Lowercase x Shows Trial Assessments Not Considered as Endpoints.

Trial Epoch	Life-style Changes	(Start of) Active Run-in	(Start of) Washout	Randomized Trial Period				
				V4 (baseline-RT)	V5	V6	V7	V8
Visit	V1	V2	V3					
Week					1	4	8	12
Planned Day		-14	-7	1	8±2	28±3	56±3	84±7
Endpoints								
Primary Endpoint								
Number of nocturnal voids		x	x	x	X	X	X	X
Secondary Endpoints								
Responder rates derived from number of nocturnal voids					X	X	X	X
NI Diary Total Score		x		x	X	X	X	X
NI Diary Overall Impact Score		x		x	X	X	X	X
PGI-I					X	X	X	X
PGI-S		x		x	X	X	X	X
Bother				x	X	X	X	X
ISI		x		x		X	X	X
FUSP		x	x	x	X	X	X	X
Nocturnal diuresis rate (=NUV / Total sleep)		x	x	x	X			X
NUV		x	x	x	X			X
Safety Endpoints								
Adverse events a			X	X	X	X	X	X
Hyponatremia serum sodium level	x		x	b	X	X	X	X
Total daily urine volume		x		x	X			X
Vital signs	x	X	x	x	X	X	X	X
Laboratory values: Clinical chemistry, haematology, urinalysis	x			x	X	X	X	X
Laboratory values: Coagulation factors	x			x		X		X

Trial Epoch	Life-style Changes	(Start of) Active Run-in	(Start of) Washout	Randomized Trial Period				
				V4 (baseline-RT)	V5	V6	V7	V8
Visit	V1	V2	V3		1	4	8	12
Week								
Planned Day		-14	-7	1	8±2	28±3	56±3	84±7
Endpoints								
Exploratory Endpoints								
NPi (=NUV / Total daily urine volume)		X		x	X			X
Copeptin		X		x				X
Total sleep		x	x	x	X	X	X	X

a AEs are also recorded at a telephone follow-up scheduled at Day -10±1

b Serum Sodium is also measured at Visit 4 as a part of the standard laboratory measurements

For post-randomization Voiding Diary endpoints, the date of completion of the diary (Night 3), will be used for the allocation of the data according to the visit windows. For all other endpoints including pre-randomization Voiding Diary data, the corresponding actual site visit day will be used for the allocation of the data according to the visit windows. The analysis day (ADY) is defined as date of corresponding site visit (Night 3 for post-randomization Voiding Diary data) – date of Visit 4 (day of randomization / baseline of the double-blind treatment period). Visit 4 is defined as Analysis Day 0 and has no visit window for the corresponding site visit date.

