## 6 Trial population

### 6.1 Demographics and Other Baseline Characteristics

#### 6.1.1 General Considerations

The trial has two baselines, one for the enrichment period (denoted baseline-ENR) including the latest data obtained before or at Visit 2, and one for the randomized-treatment period (denoted baseline-RT) including the latest data obtained before or at Visit 4 unless otherwise specified.

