Lowest observed change from baseline-RT in Serum Sodium				Alternative safety indicator for therapeutic window	
Incidence and severity of Adverse Events	Section 11.3.1				
Adverse Event of Special Interest: Hyponatraemia Episodes	Section 11.2.1				
Clinically significant changes in laboratory values and vital signs	Sections 11.3.2 and 11.3.3				

a Endpoint assessed at Weeks 1, 4, 8 and 12.

b Endpoints are derived using all diary data collected during the treatment period.

c Endpoint assessed at Weeks 1 and 12.

d Correlation between changes in FUSP and total sleep time at Weeks 1, 4, 8 and 12.

e This questionnaire is retrospective and raw scores will be used in the analysis (not changes from baseline) and the ANCOVA model will not be adjusted for baseline value.

f Endpoint assessed at Weeks 4, 8 and 12.

g Correlation with NPI at Visit 2.

h Endpoint assessed at Week 12.

Illustration of the therapeutic window is described separately in Section 10.4 and safety related endpoints are further described in Section 11.

Explorative analyses by sex are planned for all endpoints, including correlation analyses. For these the following are noted:

- Estimates of the sex-specific dose-response for the aggregated averages after 12 weeks of treatment will follow the Bayesian analysis described in Sections 10.2.1 and 10.3.3 by conducting a separate analysis for each sex. Possible differences between the sex-specific models will be investigated.
- The regression models will be supplemented with an analysis considering sex as well as all interactions between sex and the effects specified in the all-subjects analysis, including any interaction terms specified in the all-subject analysis. Possible differences between the treatment effects for men and women will be evaluated by the treatment-by-visit-by-sex (treatment-by-sex for single-visit outcomes) interaction term with the effect of treatment-by-visit (treatment for single-visit outcomes) included in the model.

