#### 10.3.6 Treatment effects on single-time-point quantitative variables

Treatment effects on single-time-point quantitative variables will be analysed using SAS PROC MIXED to perform an ANCOVA (a non-parametric dose-response curve is assumed). For the percentages of nights with response, the systematic effects will comprise treatment as a categorical variable and baseline-RT number of nocturnal voids minus 2 as a linear covariate. For change from baseline-RT in copeptin, the systematic effects will comprise treatment as a categorical variable and the baseline-RT level minus 13.1 as a linear covariate. For change from baseline-RT to lowest observed serum sodium, the systematic effects will comprise treatment as a categorical variable and the baseline-RT level minus 135 as a linear covariate. The treatment contrasts (with associated 95% confidence intervals without multiplicity adjustment) versus placebo will be tabulated and graphically illustrated. The analyses will be applied to the observed data on the ITT-RT analysis set. For change from baseline-RT to lowest observed serum sodium, the analyses will be performed both using randomized treatment for the observed data on the ITT-RT analysis set for comparability with the results for the efficacy variables and using actual treatment for the Safety-RT analysis set for comparability with the analyses of episodes of hyponatraemia based on observed serum sodium.

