### **13 Risk-benefit assessment**

Risk-benefit will be evaluated based on the graphical illustrations of the therapeutic window (Section 10.4).

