In addition to the illustrations of the therapeutic window specified in the protocol, illustrations of the therapeutic window will be produced using the estimated treatment contrast compared to placebo for the change from baseline-RT to lowest post-baseline measurement of serum sodium as the safety indicator. The inclusion of desmopressin in the plots illustrating the therapeutic window (“Corresponding efficacy and safety of desmopressin will be illustrated in a side panel for comparison.”) has been deleted to comply with “None of the primary, secondary or explorative analyses will include desmopressin.” (Section 10.1).

In the analyses of time to ‘confirmed’ hyponatraemia episodes, the time to event is defined as the time of confirmation in stead of the time to first measurement below the threshold to avoid conditioning on the future. The protocol states “The associated relative hazards of treatment and gender will be analysed using Cox proportional hazards model adjusting for baseline serum sodium and age (<65,  $\geq$ 65 years). Possible heterogeneity between the genders in the relative treatment hazards will be explored by the inclusion of a treatment-by-gender interaction term”. These analyses will not be performed since the trial is too small to perform Cox regression analyses of the occurrence of hyponatraemia events with 9 treatment groups and 2 covariates.

The adverse events tables presenting incidences of least 5% have been changed to presenting at incidences of at least 10% because it is expected that for several of the FE 201836 treatment groups, 20 subjects or less are allocated to the group.

According to [REDACTED], the interim analyses will deviate from the Appendix 2 in the protocol regarding the derivation of the allocation probabilities by the factor  $1/(n_d + 1)$  before the normalization to sum to 1.

Remaining changes are all considered clarifications of presentations specified in the protocol.

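### SAP 10.4 takes the supplementary sodium indicator from baseline-ENR where the rest of the SAP uses baseline-RT; as a lesser point, the Kaplan-Meier sodium plots stop at day 85, inside the Visit 8 window

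*SAP*

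**What the plan says.** **Baseline.** SAP 10.4 specifies extra therapeutic-window figures that use the estimated contrast with placebo "for the change from baseline-ENR to lowest post-baseline measurement of serum sodium as the safety indicator". Three other places in the SAP describe the same quantity:

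- Table 5 lists "Lowest observed change from baseline-RT in Serum Sodium" as the alternative safety indicator for the therapeutic window.
- Section 10.3.6 gives the model: "For change from baseline-RT to lowest observed serum sodium, the systematic effects will comprise treatment as a categorical variable". The baseline-RT level minus 135 is the covariate.
- Section 14 describes the added figure as using the contrast "for the change from baseline-RT to lowest post-baseline measurement of serum sodium as the safety indicator".

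SAP 6.1.1 defines two baselines, "one for the enrichment period (denoted baseline-ENR) including the latest data obtained before or at Visit 2" and a second one (baseline-RT) from the latest data at or before Visit 4. SAP 13 bases the risk-benefit judgement on the 10.4 figures.

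**Kaplan-Meier limit.** SAP 11.2.1.3 censors every subject in the Kaplan-Meier sodium plots at the End-of-Trial Visit or 85 days after randomisation, whichever comes first. For confirmed episodes the event date is the date of confirmation. The protocol flow chart and SAP Table 3 allow Visit 8 at 84±7 days. SAP Table 4 gives sodium at Visit 8 an analysis window from day 71 with no upper end. The same SAP section also says that Kaplan-Meier plots are not fully suitable for these visit-grouped data, and it adds life-table curves.

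**The concern.** **Baseline.** A supplementary figure that feeds the risk-benefit judgement has two definitions. The two baselines are different samples. The protocol schedule reads "Blood samples for analysis of serum sodium will be collected, preferably in the morning, at Visits 1, 3, 5, 6, 7 and 8", so there is no planned sodium at Visit 2, and baseline-ENR is the Visit 1 value or its re-test. For baseline-RT a value does exist: "Serum Sodium is also measured at Visit 4 as a part of the standard laboratory measurements". Section 10.4 also leaves open which samples count as post-baseline. After a baseline before Visit 2, that phrase could take in Visit 3, when every subject, including those later given placebo, has been on 500 µg. A placebo nadir could then be a value measured on active drug.

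**Kaplan-Meier limit.** A first low sodium found at an on-schedule Visit 8 after day 85 is drawn as event-free, while the incidence and life-table displays in the same section count it. The plots of one set of events would then disagree, partly because of when Visit 8 happened to be booked.

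**Working it through.** **1. Baseline: the passages side by side**

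| SAP place | Role | Baseline |
|---|---|---|
| 10.4 | defines the figure | ENR |
| Table 5 | lists the indicator | RT |
| 10.3.6 | ANCOVA that gives the contrast | RT (change and covariate) |
| 14 | describes the added figure | RT |

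No analysis in the SAP gives a baseline-ENR contrast for lowest sodium, so the figure cannot be produced from 10.3.6 as 10.4 words it.

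**2. Does the label change the contrast?** Write a subject's level as S, the randomised effect as Δ (0 on placebo), the run-in effect as Δ500 and the sample errors as e.

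- Nadir over Visits 5-8: S − Δ + min(e5,…,e8). Either baseline is measured before randomisation, so its mean is the same in both arms. The expected contrast is −Δ with either label.
- Nadir that also includes Visit 3: min{S − Δ500 + e3, S − Δ + min(e5,…,e8)}. On placebo the first term is often the smaller, which pulls the placebo nadir down. On active drug it does so less. The contrast shrinks toward zero.

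Illustration. All sodium values are assumptions: between-subject SD 2.5, within-subject SD 1.5-3 and a 500 µg drop of 0.5-3, all in mmol/L. Subjects must have Visit 1 ≥135 and Visit 3 ≥130. ANCOVA with 300,000 subjects per arm gives the ratio of the baseline-ENR contrast to the baseline-RT contrast:

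| Samples in the nadir | Dose | Ratio |
|---|---|---|
| Visits 5-8 | all | 0.98-1.01 |
| Visit 3 and Visits 5-8 | 500 µg | 0.51-0.79 |
| Visit 3 and Visits 5-8 | dose with half the effect | 0.36-0.76 |

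With within-subject SD 2 and a drop of 2, the baseline-RT contrast at 500 µg is −2.00 and the ratio with Visit 3 is 0.66.

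**3. Kaplan-Meier: days beyond the limit**

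- SAP convention (Visit 4 = analysis day 0): 84 ± 7 gives days 77-91. Days 86-91 are 6 of 15, or 40%.
- If Visit 4 is Day 1: analysis days 76-90. Days 86-90 are 5 of 15, or 33%.
- With Visit 8 dates assumed uniform, or normal around the planned day with SD 2-4, 11-40% of visits fall after day 85.

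**4. Height of the last step.** Let q be the true share of subjects with a first low value at Visit 8 and D the Visit 8 day. If event-free subjects leave on their own Visit 8 day, the step is

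1 − Π[1 − q·P(D = d)/P(D ≥ d)].

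For uniform dates on days 77-91 the ratios P(D = d)/P(D ≥ d) are 1/15, 1/14, …, 1.

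- Up to day 85: 1/15 + … + 1/7 = 0.868, so the step is about 0.85-0.86 q for q = 5% and 2%.
- Over all days: 1/15 + … + 1 = 3.318, so the step is about 3.1-3.2 q.

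Across the assumed date distributions, both day conventions and q of 2% and 5%, the step is 0.85-1.74 times q as written and 3.1-5.4 times q if the limit is simply deleted. Holding event-free completers to a common day gives 1.00 in simulated arms of 50 and 100.

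**5. Confirmed episodes.** Protocol 7.1.3.1 sets re-tests 5±2 days apart, so the second test comes 3-7 days and the third 6-14 days after the first. A mild or moderate episode first seen at the End-of-Trial Visit is therefore confirmed after the subject has been censored, and cannot appear in the confirmed-episode plots.

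**The case against.** **Baseline.** The best reply is that 10.4 contains a one-word slip which the SAP itself resolves. The figure plots a contrast, only 10.3.6 produces it, and that model uses baseline-RT. Nor is a pre-run-in baseline foreign to the SAP. Section 11.3.2.2 sets the laboratory baseline as the last value before first dose, 11.2.1.3 counts episodes after baseline-ENR, and 11.2.1.2 and 11.3.2.3 use both baselines. This largely stands and is why the point is minor. It does not remove the conflict, because those sections do not describe this contrast and the three that do agree on baseline-RT.

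A reader might infer that the plan as written understates the sodium risk in its risk-benefit figures. The documents do not support that. Shrinkage needs the further step of counting Visit 3 in the nadir, which no specified analysis does, and its size rests on assumed SDs and effects.

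**Kaplan-Meier.** The SAP already concedes the weakness of these plots and supplies life-table curves with no day-85 limit. The plots are descriptive, carry no test and lie outside SAP 13. All of this stands. A reader might infer that late hyponatraemia is lost from the trial's results. It is not: a first low value after day 85 still enters the by-visit tables, the incidence and the life-table curves, and one by day 85 also enters the first-observation Kaplan-Meier plots. Nor is the limit purely harmful, since deleting it alone distorts the last step more than keeping it.

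**Conclusion.** Both points hold as minor corrections.

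1. Section 10.4 names the wrong baseline for a supplementary figure. The textual conflict is certain. There is no expected effect on the contrast if only post-randomisation values enter the nadir, and bias toward zero if Visit 3 enters. The size of that bias cannot be taken from the documents.
2. The day-85 limit lies inside the permitted Visit 8 window under either day convention and excludes 5 or 6 of its 15 days. The share of visits affected, 11-40%, depends on assumed visit dates. The harm is inconsistency between descriptive displays.

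Neither point affects the primary analysis, the 10.3.6 ANCOVA, the Safety-RT sodium summaries or the main window plots of sodium <130 and ≤125 mmol/L. Those plots count events at or before 12 weeks and are not governed by the day-85 rule.

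**What to change.** **Section 10.4.** Replace baseline-ENR with baseline-RT and define the nadir as the lowest post-randomisation value. This costs one sentence and no data.

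**Section 11.2.1.3.** Make the life-table curves the main display. If the Kaplan-Meier plots are kept:

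- Set the limit no earlier than day 91, and hold event-free completers to a common day, the later of that limit and the latest observed event. SAP 7 does the same for completers in its discontinuation curves. Early withdrawals stay censored at their End-of-Trial Visit.
- In the confirmed-episode plots, count confirmatory re-tests after any End-of-Trial Visit, including an early one. Otherwise episodes first seen at that visit remain lost.
- State the cost. The parallel with SAP 7 is imperfect: a completer cannot later discontinue, but here event-free status is carried forward without a test. In the first-observation plots that is a matter of days, at most 91 − 77 = 14 for on-schedule visits. In the confirmed-episode plots an event could fall at 91 + 14 = day 105, so a completer seen on day 77 would be carried 28 days.

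No new data are needed.

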## 10.5 Explorative Benchmarking Analysis

The explorative benchmarking analysis will descriptively summarize aggregated as well as visit-specific changes from baseline and percentage changes from baseline in number of nocturnal voids by all treatment groups, including desmopressin, for each visit in the randomized-treatment period. The summary statistics will include 95% confidence limits for simple means. No imputations will be done for this analysis which will be based on the observed cases only. Tables and figures will be produced as appropriate. This analysis will also be repeated by sex.

Similar tables will be produced for the quantitative, secondary endpoints: percentage of nights during treatment period with at most one nocturnal void, percentage of nights during treatment period with complete response, change from baseline in NUV, change from baseline in FUSP, change from baseline in nocturnal diuresis rate, change from baseline in NI Diary Total Score, change from baseline in NI Diary Overall Impact Score, PGI-I urinary symptoms score, change from baseline in PGI-S score, change from baseline in Bother as measured by the Hsu 5-point Likert Bother Scale, change from baseline in ISI.

Frequency tables by treatment for each visit will be produced for the categorical, secondary endpoints: response defined as 50% reduction in nocturnal voids from baseline based on aggregated average change from baseline, and response defined as 50% reduction in nocturnal voids from baseline based on visit-specific change from baseline.

## 11 Safety

### 11.1 General Considerations

#### 11.1.1 Analysis Sets

Safety analyses with respect to the enrichment period will be based on the Safety-ENR analysis set, while analysis with respect to the randomized-treatment period will be performed using the Safety-RT analysis set. For calculation of percentages, the denominator will be the total number of subjects in the treatment group in the corresponding safety analysis set.

All analyses will be based on the actual treatment received.

